Few studies have examined the effectiveness of an exercise training program coupled with a memory training program. Given the success of exercise programs with healthy older adults and evidence of some positive effects of in MCI patients, it is important to determine if alternative approaches, such as water-based activity, will extend the benefit for those individuals in whom weight-bearing exercise is not possible. The knowledge gained from this proposal will lay the groundwork for a large-scale clinical trial testing hypotheses about the efficacy of nonpharmacological interventions that target cognitive impairment in persons with MCI. The goal of pilot work is to ascertain that the proposed methods are adequate for a large-scale clinical trial in terms of recruitment and retention of appropriate subjects, inclusion and exclusion criteria, appropriateness of treatment condition, and measures.

The aims listed below will be tested in a two-phase single-arm trial conducted at the VA Palo Alto Health Care System (VAPAHCS) that will include: 1) a physical exercise phase and 2) a cognitive training phase. The six-month exercise phase will consist of non-weight bearing water-based physical exercises. After the six-month exercise phase, veterans will complete a two-week cognitive training program. This two-year proposal will include 50 veterans with MCI aged 50 years to 90.

**Specific Aim 1:** To determine the feasibility of a randomized, controlled trial combining physical activity + cognitive training in persons with MCI as shown by good recruitment and retention rates.

**Specific Aim 2:** To evaluate the appropriateness of suggested inclusion and exclusion criteria for the aims of the proposed project.

**Specific Aim 3:** To evaluate appropriateness of the water-based physical exercise + cognitive training (WATER + CT) conditions for study goals.

**Specific Aim 4:** To assess the ability of selected outcome measurement techniques to determine the efficacy of WATER+CT.

**Specific Aim 5:** To examine outcome "moderator" and "mediator" measurement techniques to determine: a) in whom and under what conditions clinically relevant change occurs and b) the mechanisms through which clinically relevant change occurs.

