CT: All participants will complete a four-week CT course after the six-month exercise phase. The CT will follow the format of a “comprehensive extended” training developed in our earlier work (Fairchild et al., 2010; Yesavage et al., 2008). Training procedures include non-mnemonic “pre-training” combined with mnemonic training. This includes six hours of pre-training in a classroom-type setting (two hours/day) consisting of imagery training, semantic elaboration training, and relaxation training. Once pre-training is complete, all participants com-

plete ten hours of mnemonic training in: 1) list-learning mnemonic and 2) name-face mnemonic. **Method-of-Loci mnemonic**: This mnemonic involves associating a list of words to a fixed list of places (or “loci”).

**Name/face mnemonic**: This mnemonic involves learning faces and names through a three-step technique: 1) choosing a prominent feature of persons face, 2) developing a concrete high imagery transformation of person’s name, and 3) forming a visual image that associates the facial feature with the name. **Design Considerations**: Selection of a single-arm trial was based upon the purpose of the study, which is to establish feasibility of the intervention. Thus a direct comparison group is not needed at this time; however, should this intervention be shown feasible, an active control would be appropriate for inclusion as a direct comparator. A parallel-groups design was chosen so the effect of water-based exercise could be determined separately from that of the CT, thus allowing for preliminary evaluation of water-based exercise alone as an augmentation strategy.

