Specific Aim 1: WATER+CT will be feasible as shown by good recruitment and retention rates. Statistical Analyses: To test feasibility of the proposed project, the ratio of enrolled to completed participants will be calculated;  $\geq 80\%$  will be considered good retention. Specific Aim 2: To evaluate the appropriateness of suggested inclusion and exclusion criteria for the aims of the proposed project. Statistical Analyses: We will examine the reported adverse events for participants as well as reasons for screening failures (i.e., those who are consented but excluded from participation prior to randomization). Descriptive analyses of these data will include frequency tables and be used to provide justification for the proposed inclusion and exclusion criteria or to modify them appropriately. Specific Aim 3: To evaluate appropriateness of the WATER+CT for study goals. Statistical Analyses: Appropriateness of treatment conditions will be determined through examination of the participant adherence data. Adherence data will include information from pedometers, heart rate monitors, 7-day activity logs, and cognitive training homework logs. Adequate adherence to exercise prescriptions and CT homework will be defined as completion of  $\geq 80\%$  of assignments as defined by self-report and trainer observation. Specific Aim 4: To assess outcome measurement techniques for participant rate of response in WATER+CT. Statistical Analyses: As this is a single-arm trial, a direct comparison between the WATER + CT condition and a comparative condition is not possible. Participants response rate will be determined by examining the percentage of participants who evidence clinically relevant change after study participation. To determine what a clinically relevant difference in the primary outcome measure (delayed recall of a Word List) would be, we reanalyzed data from our initial clinical trial (Yesavage et al., 2008). Our strategy was to look in that study at the difference in baseline scores between 60 year olds and 70 year olds on the same measure as the proposed work. We found that the difference was 1.7 words. We believe that showing such a difference would be clinically meaningful insofar as it represents a decade of aging's effects on memory. This will be an intent-to-treat analysis, thus all data will be analyzed. Specific Aim 5: To examine outcome "moderator" and "mediator" measurement techniques to determine: a) in whom and under what conditions clinically relevant change occurs and b) the mechanisms through which clinically relevant change occurs. Here we are referring to within subjects effects. Statistical Analyses: Multiple regression modeling will be performed in a preliminary manner to examine individual differences in treatment response depending on baseline (T1) characteristics (age, level of education, APOE and BDNF genotypes). A significant Response Rate X Moderator interaction indicates a differential response rate, e.g., the response rate depends upon age. Such measures are "moderator" variables, i.e., they are used to determine on whom or under what conditions improvement occurs. Additional analyses will be performed to examine the extent to which individual differences in the efficacy of CT treatments depend upon changes in cardiovascular functioning, BDNF plasma levels, and changes in efficiency of working memory (Digit Span) during combined aerobic and resistance exercise training (T1 to T3). These analyses use changes in these two measures as "mediator" variables, i.e., they are used to determine how or why improvement occurs.

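### Aim 5 sets a treatment-moderation test that a single-arm trial cannot supply; its regression can identify only baseline predictors of change

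*Combined protocol and SAP*

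**What the plan says.** Aim 5 (02. Specific Aims) seeks to learn "in whom and under what conditions clinically relevant change occurs". The method is in Database Management and Planned Statistical Analyses, under Specific Aim 5: "Multiple regression modeling will be performed in a preliminary manner to examine individual differences in treatment response". Four baseline variables are named for this: age, education, and the APOE and BDNF genotypes. The decision rule follows: "A significant Response Rate X Moderator interaction indicates a differential response rate, e.g., the response rate depends upon age". The baseline variables are labelled moderators, and "they are used to determine on whom or under what conditions improvement occurs". There are two qualifiers: the modelling is called preliminary, and the plan adds "Here we are referring to within subjects effects". T1 word-list recall is not among the listed baseline variables.

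On the comparator, Aim 4 in the same section says: "As this is a single-arm trial, a direct comparison between the WATER + CT condition and a comparative condition is not possible". Research Design, under Design Considerations, says "Thus a direct comparison group is not needed at this time" and leaves an active control for a later study. Scattered references to randomizing, and one to a parallel-groups design, do not change this. No second arm is described anywhere.

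**The concern.** A moderator of treatment is a baseline variable across which the treatment effect differs. Estimating that needs a treatment contrast at each level of the variable, and here there is none. The rule as written crosses the outcome with a covariate, so an analyst cannot carry it out literally. The nearest model that can be fitted estimates something else.

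What is at stake is the reading of the result. A significant age or APOE coefficient would, by the plan's own rule, be reported as showing in whom the programme works. The same coefficient could arise because older participants or APOE carriers decline faster untreated, or because groups differ in how they respond to repeat testing.

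**Working it through.** **1. What can be estimated.** For participant i, write the T1-to-T3 change as

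change_i = treatment response_i + natural course_i + retest effect_i + error_i.

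With everyone treated, the coefficient of change on age is the sum of the age slopes of the first three terms. Nothing in the design separates them. The plan gives no figure for Aim 5 to reproduce, so the calculations below are illustrations.

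**2. Responder status does not isolate treatment.** Aim 4 takes 1.7 words as clinically relevant change. Preliminary Work gives SDs of gain on word-list delayed recall of 4.0 and 4.2 in the group's earlier cognitive training trial. Assume those SDs, normality and zero mean change:

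- SD 4.0: P(change ≥ 1.7) = 1 − Φ(1.7/4.0) = 1 − Φ(0.425) = 0.335
- SD 4.2: 1 − Φ(1.7/4.2) = 1 − Φ(0.405) = 0.343

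About 34% would be responders with no average change at all.

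**3. Natural course differing by age.** Simulation with n = 50, all completing, 2,000 replicates, and T1 recall falling 1.7 words per decade of age (the plan's contrast between ages 60 and 70). Assumed: age SD 8 years, true-score SD 2.5 words, measurement-error SD 2.0 or 2.9 words per visit. There is no treatment moderation. The table shows how often the age term has p < 0.05. In each cell the first figure is for error SD 2.0 and the second for 2.9.

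| Course differs per decade of age | Change on age | Change on age + T1 recall |
|---|---|---|
| 0.5 words | 16%, 11% | 61%, 58% |
| 1.0 words | 50%, 25% | 89%, 81% |
| 1.7 words | 90%, 62% | 99%, 97% |

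The last row is a large difference for a programme of about eight months. The first row already exceeds 5%. Adding T1 recall does not help.

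**4. Should T1 recall be in the model?** The answer depends on facts that the plan cannot know.

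*Case A: gain depends on the starting score, and age acts only through it.* If gain falls by k words per word of T1 recall, the unadjusted age slope is k × 1.7 words per decade.

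- k = 0.2: 0.34 (simulated 0.37), significant in 9% of trials
- k = 0.4: 0.68 (simulated 0.69), 17%
- k = 0.6: 1.02 (simulated 1.01), 29%

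With T1 recall in the model, the slope is about 0 and the rate about 5%.

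*Case B: true gain is equal at all ages, and T1 recall is measured with error.* The unadjusted slope is about 0, significant in about 5% of trials. The adjusted slope is −(1 − λ) × 1.7, where λ is the reliability of T1 recall at a given age.

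- Error SD 2.0: λ = 6.25/(6.25 + 4.00) = 0.610; slope −0.390 × 1.7 = −0.66 words per decade (simulated −0.66), significant in 26% of trials
- Error SD 2.9: λ = 6.25/(6.25 + 8.41) = 0.426; slope −0.574 × 1.7 = −0.98 (simulated −0.97), significant in 32%

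In Case A the unadjusted model misleads; in Case B the adjusted model does. Neither can be called correct in advance.

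**The case against.** The strongest defence is that the plan claims little. This is a feasibility pilot, Aim 5 is framed as an examination of measurement techniques, the modelling is called preliminary, and the missing comparator is disclosed. The within-subjects remark also allows a reading in which the interaction is time by baseline characteristic, which one arm can estimate. Alternate word lists (Measures) limit item-specific practice.

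Much of this stands, and it keeps the point modest. It does not change what is estimated. With two time points, a time-by-age interaction is the age coefficient in a regression of change, so it is still a predictor of change. Alternate lists do not remove natural course or familiarity with testing. The plan speaks of treatment response and nowhere limits the result to prediction.

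Three stronger readings are tempting, and the documents do not support them.

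- A reader might infer that leaving out T1 recall is an error, because the plan ties recall to age. Case B shows that adjustment can create the artefact it is meant to remove. The 1.7 words is also a single cross-sectional contrast from an earlier trial in nondemented older adults. Its size in amnestic MCI is unknown.
- A reader might infer that Aim 5 results will set eligibility or stratification in the later trial. No section says so. Revision of the criteria belongs to Aim 2, through adverse events and screening failures.
- A reader might infer that Aim 5 can show only whether the measures can be collected. That goes too far: baseline predictors of change can be estimated, though imprecisely with 50 participants.

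**Conclusion.** The point holds for the rule and its interpretation. In one arm there is no treatment term to interact with, and the planned regression identifies baseline predictors of change, not moderators of treatment. This follows from the design and needs no numerical assumption.

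The size of the possible misreading is not determined by the documents. The 11% to 90% range for a significant age term rests on the assumed variances and on an assumed age difference in untreated course of 0.5 to 1.7 words per decade. It shows that the problem can be material, not how large it will be. No single figure for bias from omitting T1 recall is justified, since its sign and size turn on measurement error and on how gain depends on starting score. The feasibility aims are unaffected.

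**What to change.** In Database Management and Planned Statistical Analyses, Specific Aim 5:

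1. Replace the interaction sentence with a regression of T1-to-T3 change in word-list delayed recall (or responder status as used in Aim 4, named in advance) on age, education, APOE genotype and BDNF genotype.
2. Report the coefficients with confidence intervals as exploratory predictors of change, and drop the term moderator for them.
3. State that they combine treatment response with natural course and retest effects, and that moderation must be tested as a treatment-by-covariate interaction in the later controlled trial.
4. As a sensitivity analysis, show the estimates with and without T1 word-list recall. Say that either can give a spurious age association, and prefer neither on the strength of its p-value.

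No new data or visits are needed, since word-list recall is the proposed primary outcome and is already assessed at T1. The cost is a narrower claim for Aim 5 and one extra exploratory model.

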## **PRELIMINARY WORK**

This work represents a collaborative effort between experts in the field of cognition and exercise training. We are currently conducting a Department of Defense (DOD) funded RCT of the effects of physical exercise and cognitive training in veterans with MCI. Based on our current work, we know that exercise training may augment the effects of CT, thereby increasing its benefit; however it is not known if non-weight bearing exercise, specifically water-based physical exercise, produces a similar effect. Data presented below highlight preliminary work relevant to the proposed project.

Studies Accomplished: Cognitive Training. With over 25 years' experience in CT, we have investigated the efficacy of a pharmacological augmentation strategy for nondemented older adults (Yesavage et al., 2008). This RCT compared two groups: 1) Donepezil + CT and 2) Placebo + CT. The overall results of the trial suggested that Donepezil did not augment the effect of CT as both groups demonstrated improvement from baseline to 52-week follow-up on delayed recall of a word-list (Donepezil + CT group: mean gain score = 4.5, SD = 4.0, p < 0.001; Placebo + CT group: mean gain score = 4.3, SD = 4.2, p < 0.001) and a name-face task (Donepezil + CT group: mean gain score = 1.2, SD = 2.7; Placebo + CT group: mean gain score = 1.6, SD = 2.7).

Studies Accomplished: Exercise Training. [name] has studied and written extensively on exercise training and its benefits for cardiovascular disease patients. Most recently he and his colleagues at VAPAHCs published the results of a randomized prospective longitudinal study of the effects of supervised combined aerobic and resistance exercise training for persons with abdominal aortic aneurysm (Myers et al., 2014). Results indicated that these methods were safe and that participants on average, increased time spent in physical activity to approximately one hour daily of modest exercise which was an improvement of ~30 - 40%. These improvements were notably greater than in similar prior exercise training studies. The authors posited that these marked improvements were partially due to the rigorous activity surveillance and case-managed approach

used in that trial. The proposed project will employ these same methods of surveillance and a case-managed approach, though coupled with water-based physical exercise.

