Ongoing Study: Exercise Training + Cognitive Training. We have successfully collaborated on the current DOD-funded project, "A Combined Training Program for Veterans with Amnestic Mild Cognitive." This project represents the merging of our interests, namely cognitive training and exercise training, towards a new target problem. At completion in September 2015, this ongoing RCT will compare the effects of a combined aerobic and resistance exercise program + cognitive training (CARE + CT) program to a stretching exercise + cognitive training (SE+ CT) program. Interim results indicate that the intervention is relatively well received by participants, as recruitment and retention rates are positive. To date, fifty-five veterans have been randomized to either the CARE+CT or SE+CT condition. Approximately 8% of those randomized have been lost to follow-up. Reasons for discontinuing study participation were largely due to development of acute illness (i.e., CVA or cancer) or injury (i.e., concussion sustained after fall) that prevented further study participation. There are no group-based differential dropout rates. *The preliminary results of this trial suggest that physical exercise does augment the effect of cognitive training as the CARE+CT group, compared to the SE+CT group, demonstrated clinically significant improvements on measures of learning (CARE+CT group: mean gain score = 13.5, SD=11.21; SE+CT group: mean gain score = 9.5, SD=9.68) and delayed recall (CARE+CT group: mean gain score = 7.25, SD=4.11; SE+CT group: mean gain score = 5.83; SD=2.69).*

Over 1500 veterans have been screened study participation and approximately 15% of those were ineligible due solely to musculoskeletal injuries and illnesses (i.e., impaired gait, osteoporosis, degenerative disc and joint disease) that prevent full engagement in weight-bearing exercises. Given the prevalence of these illnesses and injuries in veterans coupled with the increased risk of cognitive impairment, it is vitally important that we investigate methods to extend the cognitive benefit of physical exercise and cognitive training to all

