**Sample size**: One of the proposed project’s aims is to examine recruitment and retention rates for a MCI population in a treatment study. No prior research has examined a water-based physical exercise + CT intervention. To guide power analyses for the current project, studies from both the exercise training and the CT literature were examined. A meta-analysis (Li et al., 2011) of cognitive interventions for persons with MCI reported a modest effect size (0.45). The literature on effect sizes for aerobic interventions for cognitive improvement is more limited and the effects reported are less consistent, hence we assume a small effect size of (0.35), less than that expected for the CT. Using the smaller of the two effect sizes (0.35), we would need 274 participants to test the efficacy of this treatment. In the proposed feasibility study, we will randomize 50 participants over the course of the trial, which we hope will generate more accurate estimates of expected effect sizes as well as demonstrate recruitment feasibility. Ultimately we hope to demonstrate that in a larger RCT over 5 years, recruiting at the same rate, we will be able to recruit the necessary 274 participants.

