**Measures**: There are three primary time points (Time 1: Screening/Baseline, Time 2: End of Exercise Training, Time 3: End of CT) at which participants will complete cognitive, psychological, physiological, and biological assessments. Screening measures include measures of episodic memory (Logical Memory I and II from WMS-IV; Wechsler, 2008), mental health (MINI; Sheehan et al., 2002), activities of daily living (Functional Activities Questionnaire (FAQ); Pfeiffer, 1982), a semi-structured interview of cognitive impairment (Clinical Dementia Rating Scale (CDR); Morris, 1993), and assessment of risk factors for vascular dementia (modified Hachinski; Rosen et al., 1980). Measures collected during the cardiopulmonary exercise testing include the VA Prognostic Score, and Veterans Specific Activity Questionnaire (VSAQ; Myers et al., 1994), all of which will be used to estimate risk and assess suitability for exercise training (Gibbons et al., 2002; Morrow et al., 1993). The VSAQ will be used specifically to estimate exercise capacity and thus individualize the intensity during the cardiopulmonary exercise test. Veterans who are not eligible to participate because of cognitive, psychiatric, or medical issues will be referred for further diagnostic work-up or treatment to the Memory Disorders Clinic at VAPAHCs, which provides diagnostic services to older veterans. **Data collected regarding the reasons for exclusion will be analyzed to provide support for the appropriateness of the inclusion and exclusion criteria**. **Feasibility** will be assessed through examination of recruitment and retention rates. **Participant adherence**: Participants will wear heart rate monitors during exercise sessions and pedometers throughout the exercise phase of treatment. They will also log their activities on a 7-day activity recall questionnaire. Data from the pedometers, heart rate monitors and the 7-day activity recall will be collected from participants when they return for the VAPAHCs-based exercise sessions. During CT, participants will have homework and complete quizzes assessing their knowledge of the techniques. They will also complete logs tracking their use of mnemonic techniques. These quizzes and logs of homework completed will serve as measures of participant adherence during the cognitive training portion of the study. The **proposed primary outcome measure** is measure of delayed recall on a 16-item Word-List Task. Equivalent alternate lists of words will be used to counterbalance across time points. The **proposed secondary outcome measure** is recall of a 12-item Name-Face Pair Task. Both the Word-List Task and the Name-Face Pair Task have been used successfully in our prior research and have been shown to be sensitive to the mnemonics taught in the CT (i.e., Method of Loci and Name-Face Mnemonic) (Yesavage et al., 2008). **Cognitive measures** include measures of verbal learning and memory (Rey Auditory-Verbal Learning Test; Lezak, 2004), working memory (Digit Span from WAIS-IV; 2008), processing speed (Symbol Digit Modalities Test; Smith, 1991); attention (Stroop Color and Word Test; Golden 1978), and subjective memory impairment (Multifactorial Memory Questionnaire; Troyer and Rich, 2002). Self-report **measures of physical activity** include the Yale Physical Activity Survey (DiPietro et al., 1993). Finally, **biological measures** will be collected from participants. These include measures of DNA, which will be collected through blood collected at VAPAHCs. We will examine both APOE and BDNF genotypes. The APOE genotyping will be performed according to the restriction isotyping protocol of Hixson and Vernier (1990). BDNF genotyping will also be conducted in-house by [name] staff. Additionally, plasma concentrations of BDNF will be measured using

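### Aim 5 leaves its dependent variable undefined; if it is the yes/no response of Aim 4, much of the information in the word score is lost

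*Combined protocol and SAP*

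**What the plan says.** Under Database Management and Planned Statistical Analyses, Aim 4 defines response as a proportion: "Participants response rate will be determined by examining the percentage of participants who evidence clinically relevant change after study participation". It then derives 1.7 words on the primary outcome as the clinically relevant difference. Use of 1.7 as a cut-off for each person is implied, not written. The primary outcome (Research Design, Measures) is a "measure of delayed recall on a 16-item Word-List Task", so it runs from 0 to 16.

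Aim 5 announces preliminary multiple regression of individual differences in treatment response on age, education, APOE genotype and BDNF genotype. Its one rule for reading the result is "A significant Response Rate X Moderator interaction indicates a differential response rate, e.g., the response rate depends upon age". The mediator sentence that follows concerns the efficacy of CT and does not mention response rate. Aim 5 states no link function, alpha, multiplicity rule, power or precision.

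**The concern.** Response rate has a single definition in the plan, the Aim 4 percentage, and a percentage of participants needs a yes/no call per person. Read that way, Aim 5 takes a numeric score, cuts it at 1.7 words and asks whether four baseline characteristics predict which side of the cut a person falls on. Where most people pass the cut, the rarer class is small and the regression is weak.

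The interaction is a separate difficulty. An interaction with a moderator needs another factor, such as treatment arm. Here there is one arm and response is the dependent variable, so the term as written cannot be put into a model.

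The pilot is meant to inform a larger trial. Calling moderators present or absent by significance on a coarsened outcome at this sample size would miss real ones and exaggerate those that happen to pass.

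**Working it through.** The plan gives no figure for Aim 5 to reproduce. Its only sample-size figure, 274, is for a later efficacy trial and plays no part here.

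**Inputs.** Sample size: "In the proposed feasibility study, we will randomize 50 participants over the course of the trial". Dropout from the ongoing trial (Preliminary Work): "Approximately 8% of those randomized have been lost to follow-up", so 50 × 0.92 = 46 completers. Gains from the completed CT trial, word-list delayed recall in nondemented adults at 52 weeks: "Placebo + CT group: mean gain score = 4.3, SD = 4.2, p < 0.001", and 4.5 (SD 4.0) with donepezil. Gains from the ongoing MCI trial: "delayed recall (CARE+CT group: mean gain score = 7.25, SD=4.11; SE+CT group: mean gain score = 5.83; SD=2.69"; that recall test is not named. Assumed: normal gains, cut at 1.7 words, two-sided 5%.

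**Non-responders and information kept.** With z = (1.7 − mean)/SD, the non-responder share is p = Φ(z). The information kept by yes/no, relative to the continuous gain, is φ(z)²/[p(1 − p)].

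| Source | z | p | Of 46 | Information kept |
|---|---|---|---|---|
| Placebo + CT | −0.619 | 26.8% | 12.3 | 0.3294²/0.1961 = 55% |
| Donepezil + CT | −0.700 | 24.2% | 11.1 | 0.3123²/0.1834 = 53% |
| CARE+CT (unnamed test) | −1.350 | 8.8% | 4.1 | 0.1603²/0.0806 = 32% |
| SE+CT (unnamed test) | −1.535 | 6.2% | 2.9 | 0.1228²/0.0585 = 26% |
| Even split | 0 | 50% | 23 | 0.3989²/0.25 = 64% |

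**Why the even split is included.** The Background expects smaller gains in MCI than in nondemented adults. Suppose the sample-size effect sizes of 0.35 and 0.45 are read as pre-post gains in SD units (an assumption). With SD 4.2 the mean gains are 1.47 and 1.89 words, giving about 24 and 22 non-responders of 46.

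**Other denominators.** At the 80% that "will be considered good retention", 40 complete and the four sources give 2.5 to 10.7 non-responders. With all 50 analysed and 4 dropouts counted as non-responders, they give 7 to 16.

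**Power for one moderator correlated 0.4 with gain** (simulation, n = 46, gains rounded to whole words, response = gain of 2 or more): about 80% on the gain. On responder status it is about 52% with the Placebo + CT figures, 31% with CARE+CT, 23% with SE+CT and 60% at an even split.

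**Four-moderator logistic model** (simulation, 1,500 runs per scenario, one covariate correlated 0.4 with gain, two genotypes carried by 30%). With 10 to 12 non-responders, separation or non-convergence occurs in 4 to 7% of runs and power is 43 to 45%, against 77 to 79% for the linear model. Failure rises to 55% of runs at about 4 non-responders and 72% at about 2.5.

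**Limit of the continuous model.** The smallest correlation detectable with 80% power is tanh[(1.96 + 0.84)/√(46 − 3)] = tanh(0.427) = 0.40.

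**Significance rule.** Four independent moderator tests at 5% give 1 − 0.95⁴ = 19% chance of at least one false positive. Adding the three listed mediators gives 1 − 0.95⁷ = 30%.

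**The case against.** The strongest reply is that no yes/no model is planned. Multiple regression, treatment response and the planned checks of normality and equal variance all suit a continuous gain. The plan also says it means within-subject effects, so the interaction may be loose wording for a moderator's relation to change over time. This stands as far as it goes: a reader might infer that the plan commits to modelling responder status, and the documents do not establish that. They leave the outcome undefined, with the decision rule pointing to response rate.

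Two further inferences also go too far.

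- A reader might conclude that moderators and mediators cannot be estimated. For moderators, that fits only about 3 to 4 non-responders. At 11 to 12 the model usually fits but is imprecise. For mediators, the plan names no responder outcome, so the loss from dichotomising is not shown.
- A reader might take 3 to 12 non-responders as the expected range. The low end rests on an unnamed recall test, and 12 is no upper bound, because it comes from nondemented adults.

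The plan calls the analysis preliminary and claims no power for efficacy. That lowers the stakes, but a preliminary analysis still needs a defined outcome, and the significance sentence remains.

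**Conclusion.** The point holds in this limited form: the Aim 5 outcome is not clearly defined, and its interaction rule cannot be applied in a single arm. If responder status is intended, it is the weaker choice in every scenario examined. Power at correlation 0.4 is about 52% on the word-list figures and about 60% at best (an even split), against about 80% on the score. If the ongoing trial's test is comparable, only 3 to 4 non-responders would be expected and a four-moderator model would often fail.

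These sizes rest on 46 completers, normal gains, the implied 1.7-word cut and a two-sided 5% test. The preference for the continuous score does not depend on which prior gain proves right. This should be changed, but it threatens neither the feasibility aims nor the Aim 4 percentage.

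**What to change.** **Moderators.** Replace the interaction sentence in Aim 5 with linear models of T3 word-list delayed recall, in words, with T1 recall as covariate. Report each moderator's slope with a 95% confidence interval, label the results exploratory, and delete the rule that significance shows a differential response.

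**Mediators.** Use the continuous recall score here too and report estimates with confidence intervals. Match the outcome interval to the CT effect the plan asks about: T3 recall adjusted for T2 recall. The text needs tidying at the same place, since it lists three mediators but calls them two, and dates exercise-phase change from T1 to T3 although exercise ends at T2.

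**Aim 4.** Keep the responder percentage as a descriptive figure.

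**Cost.** Wording only, with no new data. Aim 5 loses a yes/no headline. The continuous model is still limited: at 46 participants it reaches 80% power only for correlations of about 0.4 or more, so the intervals should carry the message.
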